2.1 Version 7.0 Software

The Trima Accel system Version 7.0 software is intended to consolidate multiple enhanced software versions with the additional value of creating improvements relevant globally. These improvements include enhancing the leukoreduction, reducing the procedure time, and improving the overall experience for the operator and donor.

The configuration of the device (software update to Version 7.0) will be provided to the Investigator by Terumo BCT. These configurations will be within the normal operating range of the Trima Accel system Version 6.4, as cleared by the FDA. The operating range for the system flow rates, anticoagulant ratios, storage conditions, and centrifugal forces are the same as the currently cleared Trima Accel system software.

The following modifications have been made in Version 7.0 software to be used with the Trima Accel system:

1. The blood prime procedure has been modified to increase the inlet pump speed during specific portions of prime, allowing the system to reduce the time of the blood prime procedure by improving the blood flow rates through the channel during the priming process.
2. Modifications to the leukoreduction system (LRS) chamber clearing procedure to clear excess WBC content from the LRS chamber in a more efficient manner.
3. Changes to the platelet inventory recovery (PIR) phase to reduce the platelet inventory in the separation channel and LRS chamber at the end of the procedure when sufficient platelets remain.
4. The platelet collection algorithm has been modified to improve the control of the concentration of platelets delivered to the LRS separation chamber, thereby improving the leukoreduction potential of the LRS chamber.
5. The platelet collection algorithm for hyperconcentrated platelets has been modified to improve the control of the concentration of platelets within the LRS separation chamber, also improving the leukoreduction potential of the LRS chamber.
6. Improvements to the venous access pressure monitoring algorithms have been made that adjusts the draw flow rate in response to a venous access alarm (autoflow). Specifically, this algorithm allows for longer pump pauses in response to a venous access alarm by automatically lowering the flow rate and will automatically increase the flow rate when no venous access alarms occur.
7. Maintenance modifications to the software to upgrade the operating system from VxWorks 5.5 to VxWorks 6.9.

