15.4 Protocol Analysis Exclusions

Data points will be excluded from analysis in the following situations:

1. Inability to collect a complete unit due to:
 - a. Subject issues (inadequate access, reaction, needle abort, procedure disqualification upon Trima Accel device update of subject platelet count and hemoglobin or hematocrit).
 - b. Decision to stop procedure by subject, Investigator, nursing staff or operator.
 - c. Equipment failure or malfunction (unrecoverable system failure; plugged or malfunctioning filter[s]).
 - d. Protocol deviation.
2. Decision to stop the procedure due to a change in the subject platelet count (ie subject qualifies for double, however day-of platelet count is for a single platelet product and 93 single platelet products have already been collected).
3. Failure or inability to update the Trima Accel system with the actual platelet count (platelet count performed on sample taken from Trima Disposable sample pouch) AND the actual platelet count differs from the entered platelet count by more than 10%. Updating the Trima Accel system with actual platelet count from the sample pouch is standard procedure for the Trima Accel system.
4. Incomplete or incorrect collection procedure or post-collection processing that affects the primary or secondary endpoint due to:
 - a. Equipment failure or malfunction.
 - b. Subject issues (inadequate access, reaction, needle abort).
 - c. Unanticipated centrifuge stop during collection procedure.
 - d. Failure to follow collection or post-collection handling procedure outlined in the Trima Operator's Manual, and supplement(s).
 - e. Subject and procedure samples are not taken as specified in protocol.
 - f. Solution other than InterSol added to platelets prior to storage.
 - g. Results of endpoint assays are not available.

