### **3.1 Sample Size**

As specified in the FDA guidance, for up to 1 allowed failure, 93 platelet products are required to show that the proportion of platelet units with an acceptable residual WBC level is at least 95% with 95% confidence. With 93 platelet products being collected, 16 failures

or less is required to show that the proportion of platelet units with an acceptable platelet yield is at least 75% with 95% confidence.

Up to 450 healthy adult subjects will be enrolled in this study to complete 279 procedures (93 single, 93 double, and 93 triple platelet products).

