### 3.2 Study Populations

Analysis populations for this clinical investigation will be the Full Analysis Set (FAS) and Safety Populations.

For all analyses by platelet product, the platelet product type (single, double, triple, or unassigned) will be determined from the calculated platelet yield (see Section 3.3) using the following.

- If the platelet yield, rounded to the nearest tenth, is  $\geq 9.3 \times 10^{11}$ , then the product will be analyzed as a triple.
- Otherwise, if the platelet yield, rounded to the nearest tenth, is  $\geq 6.2 \times 10^{11}$ , then the product will be analyzed as a double.
- Otherwise, if the platelet yield, rounded to the nearest tenth, is  $< 6.2 \times 10^{11}$ , then the product will be analyzed as a single.
- Otherwise, if the procedure was not started, not completed or the platelet yield could not be determined for some other reason, as per the protocol analysis exclusion criteria, then the subject will be analyzed as “Unassigned”.

The Safety Population will include all subjects enrolled in this trial for whom at least 1 apheresis procedure is initiated. A procedure will be considered to have been initiated if a Trima procedure start date and time are present. The Safety Population will be used for all summaries except the primary and secondary endpoints and the derived apheresis related parameters.

Due to the design of the study, a given subject may be enrolled in the study on multiple occasions. These subjects may also qualify for the Safety Population more than once. If this occurs, the subjects will be analyzed separately for each enrollment.

The Full Analysis Set (FAS) will be defined separately for single, double, and triple platelet products and will not include any repeat subjects. The FAS for a given platelet product will consist of all collections that do not meet any of the exclusion criteria specified below. The FAS will be used to examine the primary and secondary endpoints and the derived apheresis related parameters.

Data points will be excluded from the FAS analysis in the following situations:

1. Inability to collect a complete unit due to:
  - a. Subject issues (inadequate access, reaction, needle abort, procedure disqualification upon Trima Accel device update of subject platelet count and hemoglobin or hematocrit).
  - b. Decision to stop procedure by subject, Investigator, nursing staff or operator.

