- c. Equipment failure or malfunction (unrecoverable system failure; plugged or malfunctioning filter[s]).
  - d. Protocol deviation.
2. Decision to stop the procedure due to a change in the subject platelet count (i.e. subject qualifies for double, however day-of platelet count is for a single platelet product and 93 single platelet products have already been collected).
  3. Failure or inability to update the Trima Accel system with the actual platelet count (platelet count performed on sample taken from Trima Disposable sample pouch) AND the actual platelet count differs from the entered platelet count by more than 10%. Updating the Trima Accel system with actual platelet count from the sample pouch is standard procedure for the Trima Accel system.
  4. Incomplete or incorrect collection procedure or post-collection processing due to:
    - a. Equipment failure or malfunction.
    - b. Subject issues (inadequate access, reaction, needle abort).
    - c. Unanticipated centrifuge stop during collection procedure.
    - d. Failure to follow post-collection handling procedure outlined in the Trima Operator's Manual, and supplement(s).
    - e. Subject and procedure samples are not taken as specified in protocol.
    - f. Solution other than InterSol added to platelets prior to storage.
    - g. Results of endpoint assays are not available.

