#### 3.7.3 Efficiency Analysis

##### Primary Endpoints

##### Primary Endpoint Acceptance Criteria

Parameter	Measured	Acceptance Criteria
Residual WBC Count – Single Unit	Flow cytometry; BD Leukocount™ or equivalent	Residual WBC count is $< 5.0 \times 10^6$
Residual WBC Count – Double Unit	Flow cytometry; BD Leukocount or equivalent	Residual WBC count is $< 8.0 \times 10^6$ or each component $< 5.0 \times 10^6$
Residual WBC Count – Triple Unit	Flow cytometry; BD Leukocount or equivalent	Residual WBC count is $< 12.0 \times 10^6$ or each component $< 5.0 \times 10^6$

Abbreviations: WBC = white blood cell.

Summary statistics will be provided separately for single, double, and triple residual WBC levels. The summaries will include N, mean, standard deviation, median, minimum, and maximum.

Frequencies and percentages of platelet units with an acceptable residual WBC level and the lower one-sided 95% exact binomial confidence intervals (Clopper-Pearson) will be calculated separately for single, double, and triple platelet products. If the lower one-

sided confidence interval is greater than 95%, then it will be concluded that the proportion of platelet units with an acceptable residual WBC level is at least 95% for the given platelet product.

Secondary Endpoints

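### Exclusion 4b can remove a complete, measured platelet product because of access trouble or a reaction, without a result-blind decision, and one removed WBC failure can change the primary conclusion

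*SAP*

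**What the plan says.** Both documents list four groups of exclusions from the Full Analysis Set (FAS), which is used for the primary and secondary endpoints.

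- **Item 1a** (SAP 3.2, protocol 15.4) covers failure to collect a complete unit: "Subject issues (inadequate access, reaction, needle abort, procedure disqualification upon Trima Accel device update".
- **Item 4b** covers an incomplete or incorrect procedure or processing due to "Subject issues (inadequate access, reaction, needle abort". These three reasons also appear in 1a.
- **Item 4g** covers products whose endpoint assays are unavailable.
- **The lead-in to item 4 differs.** The protocol has "Incomplete or incorrect collection procedure or post-collection processing that affects the primary or secondary endpoint due to". The SAP has no condition about an effect on an endpoint, so its exclusion is wider.

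Protocol 2.1, item 6, lists venous access monitoring among the Version 7.0 changes: "this algorithm allows for longer pump pauses in response to a venous access alarm by automatically lowering the flow rate". Protocol 6 names fewer access alarms as an aim.

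For the primary endpoint, SAP 3.1 gives the sample size per type: "for up to 1 allowed failure, 93 platelet products are required". The claim that this number is meant to support is a 95% success rate for residual WBC, shown with 95% confidence. SAP 3.7.3 says that "the lower one-sided 95% exact binomial confidence intervals (Clopper-Pearson) will be calculated" for each product type.

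Under protocol 9.4, a donor whose product was excluded may be rescreened, so an excluded data point can be replaced.

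**The concern.** Inadequate access and reactions are filed as donor problems. For access this is not clear-cut: what happens when access is poor depends on the donor's vein and also on how the software responds, and that response was changed in Version 7.0. If such a procedure still gives a complete platelet product with valid results, removing it discards information about the device under test.

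The rule also leaves room for judgement. Neither document defines inadequate access or an incorrect procedure, says who decides, or requires the decision to be made without sight of the WBC and yield results. Under the protocol wording, someone must judge whether an endpoint was affected, and the natural place to look is the result itself. No planned analysis puts the excluded products back.

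At stake is the pass or fail conclusion for each product type, because the rule tolerates only one WBC failure.

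**Working it through.** **Step 1. What 4b adds to the other items.**

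| Product | Already removed by |
|---|---|
| No complete unit, because of access, reaction or needle abort | 1a |
| Complete unit, no endpoint assay result | 4g |
| Complete unit, measured, procedure judged incomplete or incorrect because of access or a reaction | 4b only |

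The third row can arise in two ways.

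- *Platelet product finished, procedure not.* Protocol 8.1 requires concurrent plasma in at least 25% of collections. If a run is stopped for access during plasma collection after the platelet product is complete, the procedure is incomplete although the platelet results may be valid. This is an illustration: the documents do not say how often the platelet product is finished first.
- *Run cut short of its target.* A run aimed at a triple may stop early and still hold a complete single or double. SAP 3.2 assigns type by achieved yield, so without 4b this run could be analysed as the smaller type.

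The concern applies to the first kind. For the second kind, exclusion is reasonable.

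**Step 2. Reproduce the plan's rule.** Inputs: n = 93, at most 1 failure, target 95%, one-sided 95% Clopper-Pearson limit (SAP 3.1, 3.7.3). With f failures, the lower limit L solves P(at most f failures in n, failure rate 1 − L) = 0.05, so L is the 5% quantile of Beta(n − f, f + 1).

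Check at a true success rate of exactly 95%:

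P(at most 1 failure in 93) = 0.95^93 + 93 × 0.05 × 0.95^92 = 0.00848 + 0.04150 = 0.04998.

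This is just under 0.05, so the stated rule is right. With n = 92 the limit for 1 failure is 94.95%, so 93 is the smallest n that passes.

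**Step 3. Effect of one removed WBC failure.** The protocol defines the FAS as the first 93 eligible collections and the SAP as all eligible collections, so both counts are shown.

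| FAS | Lower limit | Conclusion |
|---|---|---|
| 1 failure in 93 (second failure removed and replaced) | 95.001% | pass |
| 2 failures in 93 (second failure kept, first 93 used) | 93.38% | fail |
| 2 failures in 94 (second failure kept, all used) | 93.45% | fail |

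With 2 failures, 124 products would be needed to pass. The reversal occurs only when exactly one other failure remains in the FAS. If none remains, keeping the product gives 1 in 93 or 1 in 94 (95.05%), and the type still passes.

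**Step 4. Yield.** The secondary target is that "the proportion of platelet units with an acceptable platelet yield is at least 75% with 95% confidence". The limit is 75.05% with 16 failures in 93 (pass), 73.85% with 17 in 93 and 74.12% with 17 in 94 (both fail). One product can decide this too. Under the SAP's typing by yield, this can arise only for singles, because a product typed as a double or triple has already met that type's yield criterion.

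**The case against.** The strongest reply is that 4b is conditional. The procedure or processing must have been incomplete or incorrect. If the new algorithm pauses the pump or lowers the flow as designed and the run finishes properly, nothing in 4b removes the product. This stands, and it rules out the reading that any collection with access trouble is dropped.

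A reader might also infer that the access algorithm worsens leukoreduction. The documents do not support this. Protocol 2.1 links leukoreduction to items 2, 4 and 5. Protocol 5.2 reports operator interventions for the access algorithm, not residual WBC. In protocol 5.1, all 24 hyperconcentrated products collected with the modified platelet algorithm and additional Version 7.0 enhancements were below 5.0 × 10^6 WBC per dose, although that sample is small and not specific to difficult access. The lack of a documented link limits the expected size of any effect; it is not a reason to discard measured results.

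A third tempting inference is that 4b exclusions are common because the sample was raised from 350 to 450. The amendment rationale names screen failures and Section 15.4 exclusions together and does not mention access or 4b.

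Finally, 4b has a legitimate use: it keeps truncated runs out of the smaller product types. Reactions may well produce such runs, since protocol 13.2 provides for procedures to be stopped for some adverse events. Simply deleting access and reaction from 4b would lose that protection, so the fix has to preserve it.

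The SAP also lists all eCRF data (3.7) and tabulates discontinuation reasons (3.7.2). That gives some transparency, but neither provision restores the excluded products to an endpoint analysis.

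**Conclusion.** The point holds in a limited form. As worded, 4b can remove platelet products that are complete and validly measured, on grounds that overlap with a feature changed in Version 7.0. The decision is not required to be blind to the result, and the two documents set different conditions for it.

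The size that can be shown is the threshold effect: for a product type with one other WBC failure, one excluded failure separates a limit of 95.0% from one of 93.4%, and so pass from fail. This needs no assumption beyond the plan's own rule.

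How likely this is cannot be estimated. The documents give neither the share of complete products that 4b would remove nor their WBC failure rate, so any pass probability would reflect assumed inputs only. The documents do not show that such an exclusion has occurred or that the device performs worse when access is poor.

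**What to change.** In SAP 3.2 item 4 and protocol 15.4 item 4:

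1. State that a platelet product that is complete for its targeted type and has WBC and yield results stays in the FAS when access or a reaction is the only ground for exclusion.
2. State that a run cut short of its targeted product stays out of the primary analysis, so that it is not re-typed by yield as a smaller product. This needs the targeted type for each run. Protocol 10.2.2 records Trima procedure details, but the documents do not say whether the target is among them.
3. Require all item 4 exclusions to be decided and documented without sight of WBC and yield results.
4. Use the same lead-in in both documents.
5. Add a sensitivity analysis of all measured products, and a table of excluded products by reason with their WBC results.

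The cost is wording in two documents, one further analysis and one extra table. No new measurements are needed, provided the targeted type is on record. Success rates may come out slightly less favourable.

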15.2 Outcome Measures

15.2.1 Primary Endpoint

The primary endpoint for this study is the proportion of platelet units with an acceptable residual WBC level. Counts and percentages of success rates and the lower one-sided 95% exact binomial confidence intervals will be calculated separately for success rates of single, double, and triple platelet products. If 0 or 1 failure is observed, then the confidence interval will suggest that the true success rate is at least 95% with 95% confidence for the given platelet product. This approach will be applied independently to single, double, and triple platelet products.

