### 3.4 Primary Endpoints

- Proportion of platelet units with an acceptable residual WBC level for single platelet products.
- Proportion of platelet units with an acceptable residual WBC level for double platelet products.
- Proportion of platelet units with an acceptable residual WBC level for triple platelet products.

The acceptable residual WBC level is defined as following:

For single platelet products: residual white blood cell measurement, rounded to the nearest tenth,  $< 5.0 \times 10^6$ .

For double platelet products:

- Parent container has a residual white blood cell measurement, rounded to the nearest tenth,  $< 8.0 \times 10^6$ ,
- If not met, each component residual white blood cell measurement, rounded to the nearest tenth,  $< 5.0 \times 10^6$ .

For triple platelet products:

- Parent container has a residual white blood cell measurement, rounded to the nearest tenth,  $< 12.0 \times 10^6$ ,
- If not met, each component residual white blood cell measurement, rounded to the nearest tenth,  $< 5.0 \times 10^6$ .

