### 3.7 Statistical Analysis

All data collected on the eCRFs will be presented in the listings. Missing data will not be imputed. All analyses will be based on observed data only.

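### Exclusion 4g permits a double or triple with a failing parent WBC count and missing component counts to leave the primary analysis and be replaced, and no text makes it a failure

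*SAP*

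**What the plan says.** **Endpoint.** SAP 3.4 classifies doubles and triples in two steps. The first is the parent count: "Parent container has a residual white blood cell measurement, rounded to the nearest tenth", below 8.0 x10^6 for a double or 12.0 x10^6 for a triple. The second applies only after a failed first step: "If not met, each component residual white blood cell measurement, rounded to the nearest tenth", below 5.0 x10^6.

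**Exclusion.** SAP 3.2, item 4g, takes a data point out of the FAS when "Results of endpoint assays are not available". Protocol 15.4 has the same item. Neither document defines which assays count as endpoint assays.

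**Missing data.** SAP 3.7 rules out imputation and adds: "All analyses will be based on observed data only".

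**Replacement.** Protocol 15.3 builds the FAS for each product type from the first 93 collections that are not excluded. SAP 3.2 takes all non-excluded collections, and enrolment is sized to deliver 93 evaluable products of each type. Protocol 9.4 lets a donor of an excluded product rescreen.

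**Decision rule.** SAP 3.1 takes 93 products per type, with no more than one failure, as the basis for showing that the share of units "with an acceptable residual WBC level is at least 95% with 95% confidence". SAP 3.7.3 specifies that "lower one-sided 95% exact binomial confidence intervals (Clopper-Pearson) will be calculated" separately for each product type, and the limit must exceed 95%.

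**The concern.** Suppose a double has a parent count of 8.0 x10^6 or more, or a triple 12.0 x10^6 or more, and one or more component counts are missing. It has failed the only criterion that was measured. The component counts are now the results needed to settle the endpoint, and they are unavailable, so 4g can be applied. No sentence in either document requires component assays after a failing parent, and none says that their absence is a failure.

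A product with a passing parent is accepted without component counts, so whether 4g is triggered in this way depends on the outcome already observed. The study is open-label and assays are run locally at each site (Protocol 8.1 and 11), so the parent result can be known before the handling of the product is settled. At stake is the primary conclusion for doubles or triples, where the allowance is a single failure.

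**Working it through.** **Inputs.** From SAP 3.1 and 3.7.3: n = 93 per type, at most 1 failure, threshold 95%, one-sided 95% exact (Clopper-Pearson) lower limit. From SAP 3.4: the two-step limits and rounding to the nearest tenth. The share of failing products that lose their component counts is not in the documents and is varied as an assumption.

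**Step 1: reproduce the plan's figure.** With f failures in n, the lower limit L solves P(at most f failures | n, failure rate 1 - L) = 0.05. Equivalently, L is the 5% quantile of Beta(n - f, f + 1). For f = 1 and n = 93 at L = 0.95:

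0.95^93 + 93 x 0.05 x 0.95^92 = 0.0085 + 0.0415 = 0.04998

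This is just under 0.05, so L is just above 95%. The smallest n that allows one failure is 93, as the plan states. There is almost no slack.

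**Step 2: one product reclassified.** Take a group with two failing parents, one of them without component counts.

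| Handling | Failures / n | Lower limit | Criterion |
|---|---|---|---|
| Counted as failure, n = 93 | 2/93 | 93.38% | not met |
| Counted as failure, a 94th product also evaluable | 2/94 | 93.45% | not met |
| Excluded, 93 remain | 1/93 | 95.001% | met |
| Excluded, not replaced | 1/92 | 94.95% | not met |

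One product reverses the result only if at least 93 remain after the exclusion. If both failing products lacked component counts and neither were replaced, 0/91 would give 96.76% and the criterion would be met.

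**Step 3: are such products really failures?** With rounding, a component passes if it is below 4.95 x10^6. All components can pass only if their sum is below 2 x 4.95 = 9.90 (double) or 3 x 4.95 = 14.85 (triple) x10^6. So a double parent between about 8.0 and 9.9, or a triple parent between about 12.0 and 14.85, is undetermined. Above those values the product cannot pass on its components, apart from assay error or loss at splitting.

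**Step 4: illustration of the false-pass chance.** Set the true success rate at exactly 95%. Let a share q of failing products be excluded and replaced, with n kept at 93. The apparent failure rate is 0.05(1 - q) / [0.95 + 0.05(1 - q)], and the pass chance is P(at most 1 failure in 93) at that rate.

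| q (assumed) | Apparent failure rate | Pass chance |
|---|---|---|
| 0 | 0.0500 | 5.0% |
| 10% | 0.045/0.995 = 0.0452 | 7.3% |
| 25% | 0.0375/0.9875 = 0.0380 | 12.8% |
| 50% | 0.025/0.975 = 0.0256 | 30.8% |

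**The case against.** A reader might infer that the SAP orders such a product to be dropped. It does not. The parent WBC result is available and unacceptable, and on observed data neither acceptance criterion is shown to be met, so keeping the product as a failure is an equally open reading. Item 4g also sits under a stem about faulty or unfinished collection or processing, which the protocol limits to problems affecting the primary or secondary endpoint. This stands, and it is why the point is that exclusion is permitted. The stem does not clearly block exclusion, because an unavailable assay is itself one of the listed causes and the SAP omits the protocol's limiter.

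A reader might also infer that the rule always favours the device. That goes too far: some products in the undetermined ranges would have passed on their components, and removing one of those gains nothing. What does hold is that exclusion is never less favourable than counting the product as a failure.

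It can be argued that a literal 4g would also remove products with passing parents that lack component counts, which would undo the one-sidedness. But one reading, that 4g covers the results needed to classify the product, handles both cases: component counts are needed after a failing parent and not otherwise.

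The trigger may be rare. In Protocol 5.1 all 24 hyperconcentrated products collected with additional Version 7.0 enhancements were below 5.0 x10^6 per dose. Missing data must be explained on the eCRF (Protocol 16.4.2) and all eCRF data are listed (SAP 3.7), so an exclusion could be traced. These points limit the likely size but do not settle how the product is classified.

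**Conclusion.** The point holds as a gap in the primary-endpoint rules. Item 4g, together with the observed-data rule, permits exclusion and replacement of a double or triple with a failing parent and missing component counts, and no text makes it a failure. The exclusion can remove failures or undetermined products, but not one already shown to pass on its parent count.

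The firm part of the size is the single-product reversal: 2/93 or 2/94 does not pass and 1/93 does. It rests on at least 93 products remaining, which the protocol's FAS definition and the enrolment target are set up to provide. The false-pass figures of 7.3%, 12.8% and 30.8% are illustrations for assumed losses of 10%, 25% and 50% of failing products. The documents give no such share, so these figures should not be read as an estimate for this trial. Singles are not affected, because they have no second step.

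**What to change.** 1. In SAP 3.4 and exclusion 4g (with Protocol 15.4 aligned), state that a double or triple with a failing parent count and any component count unavailable stays in the FAS as a primary-endpoint failure.
2. Limit 4g to products with no parent (or single) WBC result or no platelet yield result. Yield must stay in 4g because it is the secondary endpoint and also sets the product type (SAP 3.2).
3. List every 4g exclusion with its parent count.

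A supportive analysis that counts 4g exclusions as failures is optional and should not drive the conclusion: samples lost for unrelated reasons would be scored as leukoreduction failures, and two of them would fail a group of 93.

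The cost is a few sentences and one listing; the required 93 per type is unchanged. The downside is that the success rate may be less favourable, and a product that would have passed on its components could be counted as a failure. Obtaining component counts whenever the parent fails avoids that loss.
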